5.0 CLINICAL ASSESSMENTS

5.1.1 CONCOMITANT MEDICATIONS

All concomitant medication and concurrent therapies will be documented at Baseline/Screening, at each study visit, and at early termination when applicable, as part of routine medical care/treatment. Dose, route, unit frequency of administration, and indication for administration and dates of medication will be captured.

5.1.2 DEMOGRAPHICS

Demographic information (date of birth, gender, race) will be recorded at Screening.

5.1.3 MEDICAL HISTORY

Relevant medical history, including history of current disease and information regarding underlying diseases will be recorded at Screening.

5.1.4 PHYSICAL EXAMINATION

A complete physical examination will be performed by physician at screening.

5.1.5 VITAL SIGNS

Body temperature, blood pressure and pulse will be performed at screening.

5.1.6 OTHER STANDARD OF CARE CLINICAL PROCEDURES

- TURBT
- Axial imaging of the abdomen
- Axial imaging of the chest or 2 view chest x-rays, determined by treating physician
- Bone scan, if medically indicated
- Radical cystectomy. This will occur according to established clinical guidelines (e.g. NCCN) within 6 weeks of consenting

6.0 ADVERSE EVENT REPORTING AND DOCUMENTATION

It is unlikely any subject will experience a study related adverse event as all elements of the study are part of standard of care. However if such events occur the information regarding the occurrence will be captured throughout the study using the CTCAE v5.0 criteria. Duration (start and stop dates and times), severity/grade, outcome, treatment and relation to study device and radiation treatment will be recorded on the case report form (CRF).

6.1 Adverse Events (AE)

An **adverse event** is any symptom, sign, illness or experience that develops or worsens in severity during the course of the study. Intercurrent illnesses or injuries should be regarded as adverse events. Abnormal results of diagnostic procedures are considered to be adverse events if the abnormality:

- results in study withdrawal
- is associated with a serious adverse device effect
- is associated with clinical signs or symptoms

- leads to additional treatment or to further diagnostic tests
- is considered by the investigator to be of clinical significance

SERIOUS ADVERSE EVENT (SAE)

An SAE is defined as any AE occurring that results in any of the following outcomes:

- death
- a life-threatening adverse experience
- inpatient hospitalization or prolongation of existing hospitalization
- a persistent or significant disability/incapacity
- a congenital anomaly/birth defect

Other important medical events may also be considered an SAE when, based on appropriate medical judgment, they jeopardize the subject or require intervention to prevent one of the outcomes listed.

6.2 Unanticipated Problems Involving Risk to Subjects or Others (UPIRSO)

Any of the above-listed events could classify as a UPIRSO if they meet the following criteria:

- Unexpected in nature, severity, or frequency (*i.e.* not described in study-related documents such as the IRB-approved protocol or consent form, the investigators brochure, etc.)
- Related or possibly related to participation in the research (*i.e.* possibly related means there is a reasonable possibility that the incident experience, or outcome may have been caused by the procedures involved in the research)
- Suggests that the research places subjects or others at greater risk of harm (including physical, psychological, economic, or social harm).

6.3 RECORDING OF UNANTICIPATED ADVERSE EVENTS AND SERIOUS ADVERSE EVENTS

The Investigator will probe, via discussion with the subject, for the occurrence of UADEs, AEs, and SAEs during each subject visit and record the information in the site's source documents.

Adverse events will be recorded on the study CRF/eCRF. These events will be described by duration (start and stop dates and times), severity, outcome, treatment and relation to study drug, or if unrelated, the cause. All clearly related signs, symptoms, and abnormal diagnostic procedures results should be recorded in the source document, though should be grouped under one diagnosis. Data will be collected on logs and related CRFs or eCRFs. The clinical course of each event should be followed until resolution, stabilization, or until it has been determined that the study treatment or participation is not the cause. Serious adverse device effects that are still ongoing at the end of the study period must be followed up to determine the final outcome.

All SAEs that occur (whether or not related to study device) will be documented - the collection period for all SAEs will begin after informed consent is obtained and continue until after the completion of cystectomy.

6.4 AE SEVERITY & GRADING

The National Cancer Institute's Common Terminology Criteria for Adverse Events (CTCAE) Version 5.0 should be used to assess and grade AE severity, including laboratory abnormalities judged to be clinically significant. The guidelines shown below should be used to grade severity when the event does not fit within a term/diagnosis available in the CTCAE criteria. It should be

pointed out that the term “severe” is a measure of intensity and that a severe AE is not necessarily serious.

TABLE AE SEVERITY GRADING

Severity (Toxicity Grade)	Description
Grade (1)	Mild; asymptomatic or mild symptoms; clinical or diagnostic observations only; intervention not indicated.
Grade (2)	Moderate; minimal, local or noninvasive intervention indicated; limiting age-appropriate instrumental ADL*. *Instrumental ADL refer to preparing meals, shopping for groceries or clothes, using the telephone, managing money, etc.
Grade (3)	Severe or medically significant but not immediately life-threatening; hospitalization or prolongation of hospitalization indicated; disabling; limiting self-care ADL**. **Self-care ADL refer to bathing, dressing and undressing, feeding self, using the toilet, taking medications, and not bedridden.
Grade (4)	Life-threatening consequences; urgent intervention indicated.
Grade (5)	Death related to AE.

6.5 AE Relationship to MRI

The relationship of an AE to the study MRI should be assessed using the following guidelines in the table below

TABLE AE RELATIONSHIP TO DEVICE OR RADIATION

Definite	The AE is clearly related to the study MRI
Probable	The AE is likely related to the study MRI
Possible	The AE may be related to the study MRI
Unlikely	The AE is doubtfully related to the study MRI
Unrelated	The AE is clearly NOT related to the study MRI

Note: This includes all events that occur within 30 days of the MRI. Any event that occurs more than 30 days after the MRI and is attributed (possibly, probably, or definitely) to the agent(s) must also be reported accordingly.

Determine the prior experience (expectedness) of the adverse event.

Expected events are those that have been previously identified as resulting from TURBT and cystectomy. An adverse event is considered unexpected, for expedited reporting purposes only, when either the type of event or the severity of the event is not listed in:

- The current known adverse events listed below

TURBT Expected Adverse Events

- Genitourinary: Frequency, nocturia, acute or chronic bleeding from the bladder mucosal surface
- Gastrointestinal: Rectal irritation, bowel obstruction or bleeding, rectal ulcers, hematochezia, fistula formation, colitis, mucous-like stools
- Dermatologic: Erythema, loss of pubic hair which could be permanent
- Gynecologic: Dyspareunia, ovarian failure and sterility

Cystectomy Expected Adverse Events

- Genitourinary: urinary tract infection (UTI), septicemia, stones in conduit/neobladder, incontinence, hydronephrosis, azotemia
- Gastrointestinal: bowel obstruction, diarrhea
- Wound: infection, dehiscence, hernia

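### Section 6.5 attributes adverse events to the study MRI but judges expectedness by TURBT and cystectomy lists, so UPIRSO classification can err in either direction

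*Combined protocol and SAP*

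**What the plan says.** Section 6.5 sets the attribution target: "The relationship of an AE to the study MRI should be assessed using the following guidelines in the table below". Each of the five rows of that table, from definite to unrelated, refers to the study MRI. The table's title, however, speaks of device or radiation.

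The same section then turns to expectedness: "Expected events are those that have been previously identified as resulting from TURBT and cystectomy". For expedited reporting, an event is unexpected "when either the type of event or the severity of the event is not listed in" the lists given there. One list is headed TURBT and the other cystectomy. The TURBT list includes "Rectal irritation, bowel obstruction or bleeding, rectal ulcers, hematochezia, fistula formation, colitis, mucous-like stools" and "Dermatologic: Erythema, loss of pubic hair which could be permanent", and under gynecologic events it includes ovarian failure and sterility.

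Section 6.0 says that "relation to study device and radiation treatment will be recorded" on the case report form. Section 6.2 makes it a condition of a UPIRSO that the event be "Unexpected in nature, severity, or frequency", and it names the protocol and the consent form among the reference documents. Section 6.6 gives 10 business days to notify the IRB of such a problem.

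**The concern.** Relatedness and expectedness should refer to the same exposure. Here relatedness is to the MRI, while expectedness is defined by two operations. Section 4.0 gives gadolinium contrast intravenously during the study MRI, and inclusion criterion 11 bars patients with a contrast allergy or contraindication. The protocol therefore recognises a contrast hazard, yet its expectedness lists have no place for one.

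The TURBT list also looks as if it was written for another treatment. Permanent loss of pubic hair, ovarian failure, sterility and rectal ulcers appear beside a table titled for radiation and a recording rule that mentions radiation treatment. No radiation treatment appears in the study procedures in sections 4.0, 5.1.6 or 8.0.

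At stake is whether an event is correctly classed as a UPIRSO and so reaches the IRB on the stated clock.

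**Working it through.** No sample size, power or event rate enters this point. The check is a count of the lists, followed by a trace of each reporting route.

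**Count of listed events (section 6.5)**
- TURBT: genitourinary 3 + gastrointestinal 7 + dermatologic 2 + gynecologic 2 = 14 (15 if ovarian failure and sterility are counted separately).
- Cystectomy: genitourinary 6 + gastrointestinal 2 + wound 3 = 11.
- MRI or contrast section: 0.
- Entries with a severity grade: 0 of 25. An event can be unexpected because its severity is not listed, but no severity is listed for anything. Read literally, that could make every event unexpected; if it is ignored, only the type of event counts. Two assessors could classify the same event differently.

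**Does expectedness decide the route?**
- All SAEs, reported within 48 hours (6.6): no.
- SAEs related to the protocol, notified to the principal investigator and DSMC within 24 hours (6.7): no.
- UPIRSO, to the IRB within 10 business days (6.2 and 6.6): yes. The event must also be at least possibly related to the research and suggest a greater risk of harm.
- On-study death, within 24 hours (6.7): expected deaths are exempt, but the only example is disease progression, and the section does not refer to the 6.5 lists.

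**Direction of error on the UPIRSO route**
1. An MRI or contrast event on neither list is not listed, so 6.5 makes it unexpected. It passes the first UPIRSO criterion even if it is a recognised risk of the scan. The error is towards over-classification.
2. An event after TURBT that matches an entry which may not belong on that list is treated as expected and can fail the criterion. The error is towards under-classification.
3. An MRI or contrast event recorded under a term that is on a list can also be treated as expected, because 6.5 does not say that a listed term counts only for its own procedure. As an assumption for illustration, take a skin reaction to contrast recorded as erythema (TURBT list) or a renal change recorded as azotemia (cystectomy list).

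**The link between 6.2 and 6.5.** Section 6.2 does not cite 6.5, but it treats an event described in the protocol as expected, and the 6.5 lists are part of the protocol. It also accepts the consent form as a reference, which 6.5 does not mention. The two sections can therefore disagree about the same event.

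**The case against.** A reader might infer that, because the lists hold no MRI or contrast events, reportable MRI events are screened out. The documents do not support that. Under 6.5 an unlisted event is unexpected, so the omission by itself pushes towards more reporting.

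The erythema example can also be resisted. The term stands under a TURBT heading, and the section defines expected events as those resulting from TURBT and cystectomy. On a natural reading, a contrast reaction is not an expected TURBT event; the example needs term-matching that ignores the heading. Even then, a mild reaction might not meet the UPIRSO criterion of greater risk of harm, and the frequency and severity limbs of 6.2 could still make it unexpected. This stands: the example shows what the wording allows, not what must follow.

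Serious events are caught by routes that ignore expectedness, and 6.6 also sends significant adverse events to the IRB under local policy. TURBT is standard of care in this study, so a TURBT complication might fail the research-relatedness criterion whatever the list says. Section 3.1 likewise calls the contrast-enhanced MRI standard of care. These points stand and limit the consequence.

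The consent pages are not available and may describe MRI and contrast risks. That could settle expectedness under 6.2, but would not repair 6.5, which refers only to its own lists.

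What the objection does not remove is the mismatch itself, the ungraded lists, and radiation wording in a study without radiation treatment.

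**Conclusion.** The point holds as a low-severity defect in an operative classification rule. The expectedness reference in 6.5 does not match the exposure being attributed, its severity test cannot be applied, and UPIRSO classification can err in both directions. The exposure is mainly non-serious events and the 10-business-day IRB notice; the 48-hour and 24-hour SAE routes are unaffected.

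All 20 planned subjects are due to have the MRI, but that is the enrolment figure and not a count of affected events. The documents give no event rates, so the number misclassified cannot be estimated.

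Two assumptions remain. The radiation origin of the TURBT list is an inference from its content and from the leftover wording in 6.0 and 6.5; the documents do not state it. The shared-term route assumes that an assessor matches on the term and disregards the list heading. A claim that the rule systematically suppresses serious or MRI-related events would go beyond the text.

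**What to change.** - In 6.5, state that expectedness is judged against the reference list for the procedure to which the event is attributed.
- Add a reference list for the study MRI and contrast, consistent with the consent form, and cite it in 6.2 so that both sections use the same reference.
- Either give severity for the listed events or say how the severity part of the test is to be applied.
- Have the sponsor's clinicians verify the source of the TURBT list and decide which entries belong there.
- Reconcile the attribution table title in 6.5 and the recording rule in 6.0 with a study that has no radiation treatment.

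The cost is amendment wording and a matching change to the case report form. A few more or a few fewer events may be classed as unexpected. No new subjects, visits or data are needed.

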6.6 Reporting of SAEs

Any significant adverse event will be reported to the IRB in accordance with the standard operating procedures and policies of the local Institutional Review Board (IRB) / Independent Ethics Committee (IEC).

The IRB must be notified within 10 business days of “any unanticipated problems involving risk to subjects or others.”

The Principal Investigator must report all SAEs promptly to **within 48 hours of first becoming aware of the event**. This report will be accomplished by completing a Medwatch 3500A form which is available on the FDA website at <http://www.fda.gov>.

At the time of first notification of an SAE, the following information should be provided by the site, if available:

- Patient's study number and initials
- Date of first dose of test article
- Date of last dose of test article, if applicable
- Protocol description (and number, if assigned)
- Treatment regimen (dosing frequency, combination therapy)
- Adverse event term
- Time and date of occurrence of the event
- A brief description of the event, severity, outcome to date and any actions taken
- The seriousness criteria(on) that were met
- Concomitant medication at onset of the event
- Relevant past history information
- Relevant laboratory test findings
- Investigator's assessment of the relationship to test article

Any missing or additional relevant information concerning the SAE should be provided in a written follow-up report.

It will be left to the investigator's clinical judgment whether or not an AE is of sufficient severity to require the subject's removal from treatment. If the subject was permanently withdrawn from the study or investigational product due to an SAE, this information must be included in either the initial or follow-up SAE Report Form.

The Investigator is required to comply with applicable regulations regarding the notification of his/her IRB or Ethics Committee.

6.7 Protocol Defined Important Medical Findings Requiring Real Time Reporting

Events that are to be reported in an expedited manner that may or may not meet the definition of serious are listed below. For any of these events, the Principal Investigator and Data Safety and Monitoring Committee (DSMC) must be notified within 24 hours:

1. SAE deemed to be related to the protocol.
2. On-study deaths, including death of a research subject unless the death is expected (e.g. due to disease progression).

6.8 Deviations from the study protocol

A protocol deviation occurs when the subject or investigator fails to adhere to significant protocol requirements affecting the inclusion, exclusion, subject safety, and primary endpoint criteria. Please refer to the CSMC IRB intranet webpage to obtain IRB protocol deviation reportable to the IRB:

<https://web.csmc.edu/research-and-education/research/institutional-review-board/>

Protocol deviations for this study may include, but are not limited to, the following:

- Failure to meet inclusion/exclusion criteria
- Non-compliance by the study subject with required tests and procedures (TURBT, mp-MRI HR-DWI study, radical cystectomy, etc.)
- Failure to comply with Good Clinical Practice (GCP) guidelines
- When a protocol deviation occurs, Protocol Deviation Form detailing the events will be generated. This form will be signed by the clinical site investigator and submitted to the local IRB per institutional policy. A copy of the form will be filed in the site's regulatory binder and sent to the DSMC.

7.0 DISCONTINUATION AND REPLACEMENT OF SUBJECTS

7.1 Early Discontinuation of Study Participation

A subject may be discontinued from study treatment at any time if the subject or the investigators feel that it is not in the subject's best interest to continue. The following is a list of possible reasons for study treatment discontinuation:

- Subject withdrawal of consent (or assent) for any reason
- Because the subject is too ill to proceed with radical cystectomy
- Because the subject changes their mind about treatment and elects to not undergo radical cystectomy.
- Subject is not compliant with study procedures

- Adverse event that in the opinion of the investigator would be in the best interest of the subject to discontinue study
- Protocol violation requiring discontinuation of study
- Lost to follow-up
- DSMC request for early termination of study

If a subject is withdrawn from treatment due to an adverse event, the subject will be followed and treated by the clinical site investigator until the abnormal parameter or symptom has resolved or stabilized.

All subjects are free to withdraw from participation at any time, for any reason, specified or unspecified, and without prejudice.

Reasonable attempts will be made by the investigator to provide a reason for subject withdrawals. The reason for the subject's withdrawal from the study will be specified in the subject's source documents.

7.2 Withdrawal of Subjects from the Study

A subject may be withdrawn from the study at any time if the subject or the investigator feels that it is not in the subject's best interest to continue.

All subjects are free to withdraw from participation at any time, for any reason, specified or unspecified, and without prejudice.

7.3 Replacement of Subjects

Subjects who withdraw from the study before radical cystectomy will be replaced.

8.0 SCHEDULE OF PROCEDURES

Procedures	Screening Visit	Staging	TURBT	Cystectomy	Follow-up
Informed consent	X				
Demographic data	X				
Medical history, baseline conditions	X				
Vital signs [^]					
Physical examination	X				
Survival follow-up					Every 6 months for 3 years
Chest CT†		X			
Abdomen CT/MRI		X			
Chest x-ray†		X			
Bone scan (if indicated)		X			
Pelvis MRI		X [^]			
Pregnancy test	X				
Hematology	X				
Chemistry	X				
TURBT#			X		
Research urine			X	X	
Research blood			X	X	
Fresh frozen tissue or FFPE#			X	X	
Cystectomy					X

[^]Heart rate, systolic and diastolic blood pressure while the patient is in a seated position, and temperature.

† Patients who have received a chest CT (or MRI) need not have a chest x-ray. Patients who have findings suspicious for metastatic disease on a chest x-ray at baseline should have a confirmatory CT of the chest at baseline. Patients who have findings suspicious for metastatic disease at baseline on CT should have CT scans at follow-up tumor assessments

[^] mp-4D MRI high resolution with DWI

could be outside TURBT with FFPE tissue

9.0 DATA COLLECTION AND MANAGEMENT

9.1 DATA PROCUREMENT

- Patient medical history will be extracted from the Cedars-Sinai Medical Center EMR system.
- Pathologic (histology, grade, stage) and MRI data will be extracted from the Cedars-Sinai Medical Center EMR system.
- Biological specimens (blood, urine, tissue) will be collected during patients' visits.
- Additional information in regard to diseases status will be obtained via follow-up visits and chart review.
- Information will be kept for 5 years after completion of the study.

9.2 VARIABLES COLLECTED

The following data points/variables will be collected:

1. RNA-seq of bladder tumor
2. Imaging Measurement Tools:
 - MRI Pelvis protocol with modified sequences
 - T1 and T2 imaging (relaxation differences between tumor/tissue)
 - 3D imaging of abdomen (w/o contrast)
 - DWI multi-b value (cellularity, density)
 - 3D imaging of abdomen (w/o contrast)
 - ADC maps for slow and fast diffusion components
 - DCE-MRI (microvascular density, vascularity, vascular permeability)
 - 3D imaging of abdomen (w/ contrast)
 - Kinetic parameter maps, K^{trans} , k_{ep} , v_e , AUC
 - Fractional blood volume, v_p

9.3 SOURCE DOCUMENTS

Cedars-Sinai Medical Center EMR system will constitute source documents. In particular, EMR will be reviewed for patient demography and indication for procedure, MRI data, pathology data, clinical diagnosis information and outcomes.

9.4 DATA COLLECTION AND STORAGE

All electronic data will be stored electronically in password protected Cedars-Sinai Medical Center encrypted computers within a dedicate RedCap database. Hard copy research records will be stored in secure location (e.g. locked cabinet, office). Biological specimens will be stored in freezers at secure location (locked room or space accessible only to study team) within Cedars-Sinai BioBank.

The data will be accessible only by the study team.

On the day of consent, a de-identifier ID will be generated and assigned to each patient. The study database will not include identifiers. Only designated study team members will have the key that links the de-identifier ID with patient name, MRN or other direct identifiers.

